#### 8.3.2 Additional analyzes

A partial analysis will be carried out with the objective of evaluating safety and adherence once 4 subjects per group (33% of the sample size) have completed all the visits and study procedures. Non-

Clinical study protocol: SOPH167-0816 / I

Version: 1.0

parametric statistics will be used and the same mechanisms described will be used for the total analysis of the data.

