#### 6.5.2 Diagram of the study

An enrollment time of 30 days is estimated for the total sample.

In order to increase the safety of the participants with the use of the products under investigation, a partial analysis will be carried out following a modification to the Fibonacci method. This methodology will consist of including 33% of the total sample size (4 subjects per group, n = 8), which will complete all the visits and procedures described. Once this group of 8 subjects has finished their participation in the clinical study, a blinded analysis will be carried out. During the period in which this sub-analysis is carried out, the inclusion of new participants will be restricted. Inclusion will resume when the sponsor notifies the research center.

In addition to safety, therapeutic adherence will be evaluated and problems related to procedures will be resolved, should they arise.

[figure not shown]

Figure 1. Diagram of the study

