#### 8.3 Statistical methodology

#### 8.3.1 Analysis of primary and secondary outcome variables

The statistical analysis will be carried out by personnel of Sophia Laboratories. The statistical program SPSS version 19 (IBM Corporation, Armonk, NY, USA) will be used.

The designated personnel will be blinded to the intervention groups. The coding will be done using consecutive numbers for each intervention group.

The data will be collected and sorted in an excel sheet. Later they will be exported to the platform of the SPSS program. The variables will be categorized according to their nature.

The result of the continuous quantitative variables will be presented in measures of central tendency: mean, standard deviation and ranges. See Table 4. Scales to be used

The normal distribution of the results will be obtained by the Kolmogorov-Smirnov test.

The statistical analysis of the continuous **quantitative variables** to find significant differences (p) will be the following:

- Intra-group analysis: Wilcoxon rank test.
- Inter-group analysis: Mann-Whitney U test.

The level of difference to consider significance will be an alpha of 0.05 or less.

The result of nominal and ordinal qualitative variables will be presented in frequencies, proportions and percentages.

The statistical analysis to identify significant differences of the **qualitative variables** will be done creating 2x2 contingency tables and it will be carried out in the following way:

- Intra-group difference: McNemar or Pearson test.
- Difference between groups: test χ2 (Chi-square) of Pearson.

The level of difference to consider significance will be an alpha of 0.05 or less.

For the reporting of adverse events all eyes of those participants who were randomly assigned to an intervention group after the baseline visit will be considered. The results will be expressed in number of cases (eyes).

The final report of the results will be shown in tables or graphs, as appropriate.

It will be considered that the investigational drug is safe and tolerable when there are no clinical and statistical differences in all the variables of primary outcome, with respect to its comparator.

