#### 9.2 Preliminary analysis and early termination of the study

The partial analysis described in section **8.3.2 Additional analyzes** will allow the sponsor to make a decision about the early termination of the study in the event that the safety of the participants is compromised.

The early termination of the study will be considered in the following cases:

- 1. Presence of serious adverse events in more than 5% of the participants in each intervention group.
- 2. The competent authority (COFEPRIS) considers it for security alerts.
- 3. The Sponsor determined it for his convenience or eventualities such as: economic support, manufacturing errors, etc.
- 4. Lack of recruitment as expected.

In case the decision is the early termination of the clinical study, all the research centers will be informed within the first 24 hours by the available communication channels. Likewise, the corresponding authority in each country will be informed (if applicable) and the Ethics Committees involved.

Each research center has the obligation to inform the subjects that participate in the clinical study in a period no longer than 24 hours, after receiving the information from the sponsor. You must inform all the subjects involved in any phase of the study.

The result of the preliminary evaluation will be in charge of the Clinical Operations Management and the Medical Management of Sophia Laboratories A.S. of V.C., which will have the faculty to determine the destiny of the present protocol, according to judge convenient.

Version: 1.0

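### The partial analysis in section 8.3.2 applies the final significance tests to 4 subjects per group, where neither a non-significant nor a significant p-value says much about safety

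*Combined protocol and SAP*

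**What the plan says.** Section 6.5.2 describes a first stage "including 33% of the total sample size (4 subjects per group, n = 8"), after which inclusion is paused for a blinded analysis and resumes when the sponsor notifies the center. Section 8.3.2 times the look "once 4 subjects per group (33% of the sample size) have completed all the visits and study procedures", gives its aims as safety and adherence, and sets the method: non-"parametric statistics will be used and the same mechanisms described will be used for the total analysis of the data".

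Section 8.3.1 supplies that method. For quantitative variables: "Intra-group analysis: Wilcoxon rank test" and "Inter-group analysis: Mann-Whitney U test". For qualitative variables, in 2x2 tables: "Intra-group difference: McNemar or Pearson test" and "Difference between groups: test χ2 (Chi-square) of Pearson". Alpha is 0.05 throughout. Sidedness is not stated, nor is whether p-values are exact or asymptotic. No separate provision is made for the smaller sample. The same section calls the product safe and tolerable when no clinical and statistical differences from the comparator appear in the primary variables.

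Section 9.2 says the partial analysis "will allow the sponsor to make a decision about the early termination of the study" if participants' safety is compromised.

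**The concern.** The look stands between the first 8 healthy volunteers and the exposure of the other 16 (24 - 8). The only analysis method the plan gives for it is the set used for the final data, and most of those tests have almost no resolution at 4 per group. If section 8.3.1's rule of no clinical and statistical difference is carried over with the tests, its statistical half will usually be met by default, even when a sizeable harm is present. The opposite error is also open: Pearson chi-square on very small counts can cross 0.05 where an exact test does not. The numeric criterion in section 9.2 covers serious adverse events only. For goblet cell density, epithelial defects and the tolerability variables, the plan does not say what would count as a signal at this look.

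**Working it through.** **Inputs.** 4 subjects per group, 8 of 24 (sections 6.5.2, 8.3.2, 6.6); tests and alpha 0.05 (section 8.3.1). Two-sided testing is assumed. Exact and asymptotic p-values are both shown because the plan names neither.

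**The plan's own figure.** 4/12 = 8/24 = 33.3%, which matches the stated 33%.

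**Wilcoxon signed-rank, 4 pairs, all changes in one direction.**
- Exact: 2/2^4 = 0.125. Five pairs give 2/32 = 0.0625; six give 2/64 = 0.031, the first value below 0.05.
- Asymptotic, no ties: rank sum 10, mean 5, variance 4·5·9/24 = 7.5; z = 5/√7.5 = 1.826, p = 0.068.
- Asymptotic, all four changes identical in size: variance 7.5 - (4³ - 4)/48 = 6.25; z = 5/2.5 = 2, p = 0.0455. Partial ties give 0.059 to 0.066.

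**McNemar, 4 v 0 discordant.**
- Exact: 2·0.5^4 = 0.125.
- Uncorrected: (4 - 0)²/4 = 4, p = 0.0455.
- Continuity-corrected: (4 - 1)²/4 = 2.25, p = 0.134.

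**Mann-Whitney, 4 v 4.** There are C(8,4) = 70 arrangements.
- Complete separation (U = 0): exact 2/70 = 0.0286. Asymptotic z = -8/√12, p = 0.021.
- One inversion (U = 1): exact 4/70 = 0.057. Asymptotic z = -7/√12, p = 0.043.
- The exact test therefore needs complete separation, and the asymptotic test allows one inversion.

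Power by simulation of normal data (100,000 runs at 4 v 4; 5,000 asymptotic runs at 12 v 12):

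| Shift | 4 v 4 exact | 4 v 4 asymptotic | 12 v 12 asymptotic |
|---|---|---|---|
| 1 SD | 14% | 24% | 62% |
| 2 SD | 49% | 66% | over 99% |

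**Pearson chi-square, 4 v 4.** Each expected count is half a column total, and a column total cannot exceed 8, so every expected count is at most 4. For 0/4 v 3/4:
- Pearson: 8·(0·1 - 4·3)²/(4·4·3·5) = 1152/240 = 4.8, p = 0.028.
- Fisher: 2·C(4,3)/C(8,3) = 8/56 = 0.14.

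For 4/4 v 0/4 the two agree on significance (0.0047 and 0.0286). For 2/4 v 0/4 neither is significant (0.10 and 0.43). With assumed true rates of 10% v 50%, power is 22% with Pearson and 4% with Fisher.

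**What a clean look would show.** With 0 events in 4 subjects, the one-sided 95% upper limit for the event rate is 1 - 0.05^(1/4) = 52.7%.

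**The case against.** A reader might infer that the within-group tests can never reach 0.05. The documents do not support that. Section 8.3.1 does not require exact tests, and the asymptotic Wilcoxon and uncorrected McNemar tests can reach 0.0455. For a coarse scale such as the Oxford grade, four identical one-grade changes are quite possible. The plan also allows Pearson within groups; 0/4 before v 4/4 after gives p = 0.0047, although that ignores the pairing. The between-group tests can cross 0.05 too.

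A reader might also infer that the trial has no other way to detect harm, or that a p-value decides whether it goes on. Neither is in the text. Adverse events are reviewed at Visit 1, the final visit and the safety call (section 6.5), and serious events are notified within 24 hours (section 9.3.1.3). The blind may be opened on a serious event or a safety alarm (section 7.4.1). Section 9.2 has a count criterion that needs no test: one serious event among 4 subjects is already 25% of that group, against a threshold of 5%. The decision is left to the sponsor's judgement, and the section 8.3.1 methods also include means, ranges and frequencies. Its safety rule asks about clinical as well as statistical differences.

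Finally, this is an exploratory phase I study of two gels both labelled dexpanthenol 5%, and low power with 8 subjects is unavoidable.

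All of this stands, and it limits the point to the tests. It does not rescue them. Unavoidably low power is a reason not to test at this look, and the asymptotic routes to significance rely on approximations that cannot be trusted with 4 per group.

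**Conclusion.** The point holds for the significance tests at the partial analysis; severity should-fix. With 4 pairs, the exact Wilcoxon and McNemar tests have a floor of 0.125. Their asymptotic forms pass 0.05 only with four identical changes or with 4-0 discordance uncorrected. Mann-Whitney power is about 14-24% at 1 SD and 49-66% at 2 SD. The chi-square verdict can turn on an approximation choice the plan leaves open. This is the only planned interim analysis, but not the only safety monitoring.

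The conclusion assumes two-sided testing and normal shifts for the power figures. It also reads the translated sentence in section 8.3.2 as carrying the section 8.3.1 tests to the partial analysis. It does not assume that the sponsor would stop or resume on a p-value alone.

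**What to change.** In section 8.3.2, replace significance testing at the partial analysis with blinded per-subject listings, using the visits at which section 6.5 schedules each variable:
- goblet cell density and comfort index: baseline and final visit;
- laboratory values: screening and final visit;
- Oxford grade, symptom scores, intraocular pressure and visual capacity: baseline (or the screening value where section 6.5 lets it serve as baseline), Visit 1 and final visit.

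Add counts and ranges by coded group. Flag values against limits the protocol already defines: Table 4 where a limit is printed, and the laboratory's ranges under section 6.4.3.12. Table 4 prints no limit for visual ability or the comfort index and no cutoff for the Oxford grade; for such variables, show change from baseline. State that no p-value from the partial analysis supports the decision to resume. Have the sponsor record its own review trigger before the look and cross-reference it to section 9.2.

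The cost is one paragraph and a simple listing, with no new data or subjects. The only thing given up is p-values at the interim.

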#### 8.3.3 Population analysis and management of missing data

An analysis will be carried out by intent to treat where the data of the participants that have fulfilled two visits will be included (Basal Visit and visit 1).

# 9. Methods Monitoring

#### 9.1 Data monitoring

Monitoring visits by a site monitor of Sophia Laboratories S.A. of C.V. are intended to confirm that studies sponsored by Sophia Laboratories S.A. of C.V. they are conducted in accordance with the ethical principles that have their origin in the Declaration of Helsinki and that are consistent with Good Clinical Practices and with the applicable regulatory requirements (verifying a continuous compliance with the protocol, amendment or amendments, reviewing accounting records of the product under investigation, verifying that the personnel of the site and the facilities remain adequate to carry out the study).

The researcher must ensure that they have sufficient time, space and qualified personnel for the monitoring visits.

In order to carry out the monitoring review, it is mandatory to provide direct access to all source data and those related to the study site. The monitor will conduct a review of the CRF and a Verification of Source Documents (VDF). By VDF means the verification of the records in the CRF through its comparison with the source data that the researcher will make available for this purpose.

Regarding the CRF, the monitor will mark in each visit the screens completed and approved in case of use of electronic platform.

In accordance with the applicable regulations, Good Clinical Practices, and the procedures of Sophia Laboratories A.S. of V.C. The monitors of Sophia Laboratories A.S. of V.C. they will contact the site before the start of the study to review the protocol, the regulatory and ethical requirements of Sophia Laboratories, S.A. with the staff of the site. of C.V. When reviewing the procedures for data collection, the conversation will also include the identification, agreement and documentation of the individual data for which the records in the CRF serve as source documents.

Sophia Laboratories A.S. of V.C. will monitor the study to verify, among other things, that:

- The data is authentic, correct and complete.
- The safety and rights of the subjects are being protected.
- The study is being carried out in accordance with the currently approved protocol, any other study agreement, Good Clinical Practices and all applicable regulatory requirements.

The investigator and the head of the medical institution (when applicable) agree to allow the monitor to have direct access to all relevant documents.

Study monitoring visits will be conducted at regular intervals, depending on the recruitment rate, under the arrangements between the investigator and the sponsor. All information related to these visits will be handled as strictly confidential.

Upon completion or early termination of the study, the monitor will carry out site closure activities with the investigator or site staff, as appropriate, in accordance with applicable regulations, Good Clinical Practices, and Sophia Laboratory procedures. , SA of C.V.

After the study is closed, the researcher must keep all study records on the site in a safe place. Records should be maintained to allow easy and timely recovery, when necessary (for example, in an audit or inspection). Sophia Laboratories A.S. of V.C. will inform the investigator / institution the period of time they will have to retain these records, in order to comply with all applicable regulatory requirements. However, the investigator / institution must seek the written approval of the sponsor before proceeding to the elimination of these records. The minimum retention time will satisfy the most stringent standard applicable to that site for the study, in accordance with the provisions of the PCBs, any institutional requirements or the applicable laws or regulations, or the standards / procedures of Sophia Laboratories A.S. of V.C. The researcher / institution must notify Sophia Laboratories A.S. of V.C. Of any change in file arrangements including, without limitation, the following: file in an off-site facility, transfer of ownership of records in the event the investigator leaves the site.

#### 9.2 Preliminary analysis and early termination of the study

The partial analysis described in section **8.3.2 Additional analyzes** will allow the sponsor to make a decision about the early termination of the study in the event that the safety of the participants is compromised.

The early termination of the study will be considered in the following cases:

- 1. Presence of serious adverse events in more than 5% of the participants in each intervention group.
- 2. The competent authority (COFEPRIS) considers it for security alerts.
- 3. The Sponsor determined it for his convenience or eventualities such as: economic support, manufacturing errors, etc.
- 4. Lack of recruitment as expected.

In case the decision is the early termination of the clinical study, all the research centers will be informed within the first 24 hours by the available communication channels. Likewise, the corresponding authority in each country will be informed (if applicable) and the Ethics Committees involved.

Each research center has the obligation to inform the subjects that participate in the clinical study in a period no longer than 24 hours, after receiving the information from the sponsor. You must inform all the subjects involved in any phase of the study.

The result of the preliminary evaluation will be in charge of the Clinical Operations Management and the Medical Management of Sophia Laboratories A.S. of V.C., which will have the faculty to determine the destiny of the present protocol, according to judge convenient.

Version: 1.0

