#### 7.4 Blinding (Masking)

The blinding will correspond to the research subject and the principal investigator. In addition, the statistical analysis will be carried out in a blinded manner for the partial and final analysis.

The masking will be done using boxes in the secondary packaging identical in the two groups. Blinding for the research subject and the researcher will be done by replacing the commercial labels in the case of the comparator in the tubes and the use of identical labels that contain the assignment number.

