#### 7.4.1 Opening of blinding

Blinding may be opened in the following cases:

- 1. Presence of a serious adverse event.
- 2. Safety alarm due to the use of the drugs under study.
- 3. In case the sponsor determines it for any security reason or other reason that it considers pertinent

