- D. In the research site or in the hospital with the greatest resolving power (1st, 2nd or 3rd level of medical attention). In such a way that, in case the patient is sent by the Investigator to a hospital, he / she attends by means of a reference system, it can be with an identification card that the patient belongs to the present investigation and there is an official number or folio, which pertains to the emergency care agreement with the health institution with the greatest resolving power, or a medical reference note issued by the principal investigator, so that appropriate care is given to the participating patient. It should be noted that the Study Sponsor, Sophia Laboratories, S.A. C.V., will pay the expenses for the medical care of the participating patient, only if the adverse event, adverse reaction or suspected adverse

- reaction to medication is associated or found in relation to the investigational product or investigational medication.
- E. Taking the clinical information collected, either during the care provided at the research site or provided by the treating physician (s) in the hospital, the principal investigator records the adverse event, suspected reaction adverse or adverse reaction to medication in your clinical note of the clinical record, indicating the seriousness, intensity (mild, moderate or severe), relationship with the investigational product or medication, as well as:
- F. The migration of the relevant data to the case report format and to its respective adverse event section; noting the pertinent information, already referred to in section 9.3.1.1., this in virtue of the fact that in cases of serious adverse events, which must be notified in less than 24 hours after the moment in which the principal investigator has knowledge of the same, the clinical monitor of the study is informed, so that in turn he / she informs the Scientific Committee and the Pharmacovigilance Department of the sponsor and later he / she informs the Research Ethics Committee. Regarding non-serious adverse events, these will be recorded and adequately addressed and the corresponding regulatory entity will be informed about the safety profile of the investigational product or investigational medication in the final report of the clinical trial.

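### The only numerical safety criterion for early termination, read literally, needs serious adverse events above 5% in both arms, so harm confined to PRO-167 cannot meet it; *each* should be *either*

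*Combined protocol and SAP*

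**What the plan says.** Section 9.2 says that the partial analysis lets the sponsor decide on early termination "in the event that the safety of the participants is compromised". It continues "The early termination of the study will be considered in the following cases" and lists four:

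1. "Presence of serious adverse events in more than 5% of the participants in each intervention group"
2. safety alerts from the competent authority
3. the sponsor's own convenience or eventualities
4. insufficient recruitment

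Only the first carries a number or refers to serious adverse event counts. The other relevant provisions are:

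- **Arm sizes.** There are 12 subjects per group (section 6.6), and the partial analysis takes place after 4 per group (sections 6.5.2 and 8.3.2).
- **Enrolment pause.** Recruitment is held during the partial analysis: "Inclusion will resume when the sponsor notifies the research center" (section 6.5.2).
- **Blinding.** Section 7.4 says "the statistical analysis will be carried out in a blinded manner for the partial and final analysis", and section 8.3.1 says "The coding will be done using consecutive numbers for each intervention group".
- **Individual serious events.** Section 7.4.1 lists "Presence of a serious adverse event" as a ground for opening the blind. Section 9.3.1.3 covers serious events, "which must be notified in less than 24 hours" of the investigator learning of them.

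**The concern.** As worded, criterion 1 joins the two arms with a logical AND. Excess harm from the test product alone is the pattern a controlled phase I safety study most needs to catch, and an AND rule cannot register it. The comparator is a marketed gel, and section 5.4 expects dexpanthenol to carry essentially no risk of serious events. On the protocol's own expectation, then, the comparator arm would rarely supply its half of the condition, whatever happened on PRO-167.

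At stake is whether the one pre-stated numerical criterion can work as a safety criterion. If it cannot, a decision to stop for one-arm harm rests wholly on discretion. Two people applying the criterion to the same data could also reach opposite answers, depending on how they read one word.

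**Working it through.** **Inputs from the document.** Threshold: more than 5% (section 9.2). Arm size: 12 at full enrolment (section 6.6) and 4 at the partial analysis (section 6.5.2). The document gives no derivation of the 5% and no expected serious-event risk.

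**The plan's own figures.** Section 6.6.1 takes 19 subjects and allows for 20% losses: 19 / (1 − 0.20) = 23.75, rounded up to 24, or 12 per arm at 1:1. The partial analysis covers 8/24 = 33%. Both agree with the text. The base figure of 19 was not re-derived, and nothing here depends on it.

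**What more than 5% means in subjects.**
- 12 per arm: 0.05 × 12 = 0.6, so one subject is enough (1/12 = 8.3%).
- 4 per arm: 0.05 × 4 = 0.2, so one subject is enough (1/4 = 25%).
- This holds per arm only. Pooled over 24, 0.05 × 24 = 1.2, so two subjects would be needed.

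The literal rule is therefore at least one affected subject in both arms. The either-arm rule is at least one in any arm.

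**Extreme case.** PRO-167 12/12 = 100%, comparator 0/12 = 0%. The literal rule is not met, because 0% is not above 5%. The either-arm rule is met. Affected overall: 12/24 = 50%.

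**Probabilities under assumed risks.** Let p1 be the risk in the affected arm, p0 the risk in the other arm and n the number per arm.
- P(at least one in an arm) = 1 − (1 − p)^n
- P(both) = [1 − (1 − p1)^n] × [1 − (1 − p0)^n]
- P(either) = 1 − (1 − p1)^n × (1 − p0)^n

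| n per arm | p1 | p0 | Both arms (literal) | Either arm |
|---|---|---|---|---|
| 12 | 0.10 | 0 | 0 | 0.718 |
| 12 | 0.20 | 0.01 | 0.106 | 0.939 |
| 12 | 0.30 | 0.02 | 0.212 | 0.989 |
| 4 | 0.10 | 0 | 0 | 0.344 |
| 4 | 0.20 | 0.01 | 0.023 | 0.607 |
| 4 | 0.30 | 0.02 | 0.059 | 0.779 |

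For example, with n = 12, p1 = 0.20 and p0 = 0.01: 1 − 0.80^12 = 0.931 and 1 − 0.99^12 = 0.114. Their product is 0.106, and 1 − 0.069 × 0.886 = 0.939.

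**Ceiling on the literal rule.** P(both) cannot exceed the chance of at least one event in the comparator arm. If every PRO-167 subject had a serious event and p0 were 0.01, the literal rule would be met with probability 0.11 at 12 per arm and 0.04 at 4 per arm. If p0 were 0, it could never be met.

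**Price of the either-arm rule.** With the same low risk in both arms, a review is prompted with these probabilities:
- 24 subjects: 1 − 0.999^24 = 0.024 at 0.1%, and 1 − 0.99^24 = 0.214 at 1%.
- First 8 subjects: 1 − 0.999^8 = 0.008 at 0.1%, and 1 − 0.99^8 = 0.077 at 1%.

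**The case against.** The strongest reply is about reading. The phrase may only fix the denominator, meaning that the rate is taken within a group and not pooled. The English is visibly a rough translation, and the literal reading sits badly with the stated purpose of section 9.2. That is plausible as intent, but no section says so, and a termination criterion should not depend on guessing intent.

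The second reply is that the consequence is already covered:
- Termination is only considered, and sponsor management may decide the protocol's fate.
- Enrolment pauses after the first 8 subjects.
- Each serious event is notified within 24 hours and permits unblinding.
- An affected subject is withdrawn (section 6.2.3), and a centre can be closed early (section 6.1.3).

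All of this stands. It makes 12 of 12 a logical illustration and not a forecast. It also means the study could be stopped without criterion 1. It does not make criterion 1 able to register one-arm harm.

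Third, the document expects few serious events. Both gels contain dexpanthenol 5% and are used for 10 days in healthy adults, so risks of 10% to 30% are not predictions. That is fair; they show how the two rules behave if the test formulation does prove harmful. Nor does the document establish that those who decide are blinded: Clinical Operations staff generate the allocation sequence (section 7.3), and their management shares the preliminary evaluation (section 9.2). The point does not need that blinding. An either-arm rule simply has the advantage of also working on number-coded groups.

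Last, changing an approved criterion goes through the amendment route in section 10.2, which is more than editing one word. That is correct and belongs in the cost.

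**Conclusion.** The concern holds for the literal wording of criterion 1. Serious events in one arm only, however many, do not meet it. Over the assumed risks (10% to 30% in one arm, 0% to 2% in the other), the literal rule is met with probability 0 to 0.21 at 12 per arm and 0 to 0.06 at 4 per arm. The either-arm rule is met with 0.72 to 0.99 and 0.34 to 0.78. The failure at 12 of 12 against 0 of 12 needs no assumption about risk; the probabilities rest on the assumed risks and on independence between subjects.

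It does not follow that the study could not be stopped, or that the authors meant both arms. This is a wording defect in the only numerical safety criterion, with real backstops around it. It should be corrected; confidence is medium because the looser reading may have been intended.

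**What to change.** In section 9.2, criterion 1, replace *each* with *either*. Add a clause saying that at the planned arm sizes (4 at the partial analysis, 12 at full enrolment) this means one or more subjects with a serious adverse event in an arm.

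The text change is one word and a short clause. Sample size, visits, blinding and analysis are unaffected. If the protocol is already approved, the change needs an amendment under section 10.2. The operating cost is that one unrelated serious event would prompt a review, with the probabilities given in the working (at most 0.21 over 24 subjects if the risk is 1% in both arms). That is a modest price in healthy volunteers, since the review does not oblige anyone to stop.
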